Principal Investigator

Site

Printed Name

Signature

Date

[figure not shown]
Abstract

Title	A Phase 2 Study of Preoperative Immunotherapy in Patients with Colorectal Cancer and Resectable Hepatic Metastases
Patient population	Patients with colorectal cancer (CRC) with liver-dominant or liver-only metastases who have received prior 5-fluorouracil (5-FU), leucovorin, and oxaliplatin (FOLFOX) chemotherapy and are appropriate candidates for resection of liver metastases.
Rationale for Study	We hypothesize that pembrolizumab plus vactosertib will increase tumor-infiltrating lymphocytes (TILs) and promote response without increasing perioperative complications.
Primary Objective	To characterize the change in the populations of TILs induced by neoadjuvant pembrolizumab plus vactosertib in patients with metastatic CRC.
Secondary Objectives	
To establish the safety/toxicity profile of pembrolizumab-based treatment in the perioperative setting for patients with CRC with potentially resectable hepatic metastases, including rates of perioperative complications.
 
To explore the efficacy of this strategy in this patient population. Clinical outcome measures will include response to pembrolizumab plus vactosertib as measured by R0 resection rate; pathologic response; and 1-year and 2-year relapse-free survival (RFS).

Study Design	Phase 2, single-site, open-label prospective clinical trial. See schema below. Additional cohorts exploring novel pembrolizumab-based combinations during this same perioperative window (e.g., pembrolizumab in combination with other immuno- or molecularly targeted agents, following FOLFOX) may be added and enrolled to in sequential fashion via a protocol amendment.
Number of patients	Up to 19 patients will be enrolled in the initial cohort (17 evaluable patients with paired pre-treatment biopsy and post-pembrolizumab plus vactosertib analyzable tumor specimens).
Duration of Therapy	Patients will receive a single cycle of pembrolizumab plus vactosertib prior to planned hepatic metastasectomy. Additionally, up to 8 cycles of adjuvant pembrolizumab plus vactosertib may be administered after hepatic metastasectomy.
Duration of Follow up	Patients will be followed for up to 1 year after the last dose of pembrolizumab is administered or 2 years after surgery (whichever is longer).
Duration of study	The study will reach completion 3 years from the time the study opens to accrual.

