1.1 Background on Indication

Colorectal cancer (CRC) is a major global public health problem. Approximately 1 in 20 Americans will be diagnosed with CRC in their lifetime. Metastatic CRC is the second leading cause of cancer death in the United States (US), with nearly 50,000 deaths attributed to this disease each year. The 5-year survival rate is only 13% for patients with distant metastases [1]. The liver is the most common site of metastases for CRC, occurring in ~40-50% of patients either at the time of initial diagnosis (synchronous) or at disease progression (metachronous). Due to the closed portal circulation, liver metastases from CRC are potentially resectable with curative intent, with a 5-year survival rate approaching 50% [2]. Factors that influence likelihood of cure with metastasectomy include the presence of extrahepatic disease, node-positive primary tumor, size and number of metastases, disease-free interval between original diagnosis and development of metastases, and preoperative carcinoembryonic antigen (CEA) level [3, 4]. However, progression is common and ultimately occurs in up to 75% of patients. About 30% of patients who undergo liver resection with curative intent are indeed cured, defined by 10-year survival without evidence of CRC.

Perioperative chemotherapy is now an established standard of care for patients with CRC with resectable hepatic metastases. Neoadjuvant chemotherapy can improve clinical risk scores to predict outcomes of patients with CRC liver metastases who undergo metastasectomy [5]. A Phase 3 study, European Organisation for Research and Treatment of Cancer (EORTC) Intergroup trial 40893 [6], randomized 364 patients with CRC and up to 4 liver metastases to receive either 6 cycles of 5-fluorouracil (5-FU), leucovorin, and oxaliplatin (FOLFOX) pre- and post-operatively, or surgery alone. The absolute increase in 3-year progression-free survival (PFS) associated with perioperative FOLFOX was 7.3% (35.4 vs. 28.1%; HR 0.79, p=0.058) in randomized patients, and 9.2% (42.4 vs. 33.1%; HR 0.73, p=0.025) in patients actually undergoing resection. However, the postoperative complication rate was higher in the chemotherapy arm (25 vs 16%; p=0.04); and long-term follow-up data showed no difference in median overall survival (OS) between the 2 groups (61.3 vs 54.3 months) [7].

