1.3.1 Rationale for Perioperative Pembrolizumab-Based Treatment

Identification of new strategies to augment immune-related responses in the broader population of metastatic CRC patients, without dMMR or MSI-H tumors, is essential[31]. Whereas immune checkpoint inhibitors such as pembrolizumab have shown robust single-agent antitumor activity in the ~5% of patients with metastatic CRCs harboring MSI-H or dMMR, novel strategies are needed for the ~95% of patients with MSS or pMMR metastatic CRC [8]. These strategies may include combining pembrolizumab with cytotoxic, targeted, or other immunotherapy agents.

Potentially resectable metastatic CRC represents an ideal clinical setting to assess both the clinical efficacy and immunologic/pharmacodynamics effects of pembrolizumab-based therapies, as the majority of carefully selected patients are ultimately taken to surgery following preoperative therapy (87.3% in the Nordlinger EORTC study)[6]; therefore, a large quantity of tumor tissue is available for immune cell characterization and immune/molecular profiling.

The Primary Objective of this study is to characterize change in the populations of TILs induced by neoadjuvant pembrolizumab-based therapy in patients with metastatic CRC with potentially resectable hepatic metastases. The Primary Endpoint is specifically defined as the proportion of patients with a ≥ 2 -fold increase in the TILs in post- vs. pre-pembrolizumab-based treatment tumor specimens. A ≥ 2 fold increase was the threshold used for 2 prior trials of neoadjuvant immunotherapy [28, 29]. Including a prospective study evaluating the direct immune effects of sipuleucel-T on prostate cancer tissue in the peri-operative setting. Sipuleucel-T, which was FDA-

approved for improved OS in prostate cancer, induced a >2 fold increase in TILs per unit area of tissue [28]. We believe that a doubling in immune infiltration would be deemed as biologic meaningful, whereas magnitudes of change less than that can be more arguable for publication. In two published trials of prostate cancer we have shown that neoadjuvant immunotherapies can induce a >3x increase in TILs[36]. This is in excess of the doubling with which we set the threshold in this trial.

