7.1 Evaluation of Efficacy (or Activity)

The 2-year RFS rate is defined as the proportion of patients without radiographic PD within 2 years of liver resection surgery with curative intent.

Pathologic response rate is defined as the proportion of patients with no residual cancer cells (complete response) or 1% to 49% residual cancer cells remaining (major response) in the liver resection specimen.

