8.2.2 Replacement Policy

We plan to enroll 19 patients to achieve our goal of 17 patients evaluable for the primary study outcome. If more than 2 patients turn out not to be evaluable for the primary study outcome (i.e., do not have available post-pembrolizumab-based neoadjuvant treatment tumor tissue available for analysis), they may be replaced upon discussion with the study Principal Investigator and JSC.

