8.4 Analyses Plans

8.4.1 Analysis Population

The analysis population for the primary outcome will be all patients with pre- and post-pembrolizumab-based neoadjuvant treatment tumor specimens that are evaluable for TILs.

The All Patients as Treated (APaT) population will be used for the analysis of the secondary safety/toxicity outcomes and the clinical efficacy endpoint, ORR. The APaT population consists of all patients who received at least one dose of pembrolizumab and/or vactosertib and at least one laboratory or vital sign measurement. To assess change from baseline, a baseline measurement is also required.

Patients who undergo surgical resection of liver metastases will be evaluable for the secondary clinical efficacy endpoints: pathologic response rate, R0 resection rate and RFS at 2-years.

Safety analyses will be performed for all patients having received at least one dose of pembrolizumab and/or vactosertib. The study will use the NCI CTCAE v5.0.

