8.4.3 Secondary Analysis (or Analysis of Secondary Endpoints)

The study will use descriptive statistics to report on the safety/toxicity and efficacy of pre-operative pembrolizumab-based treatment, including adverse events by NCI CTCAE (v 5.0) criteria and perioperative complications; pathologic response; R0 resection rate; and 2-year RFS. The sample size of each cohort will be too small to compare these results to historic data (i.e. from the Nordlinger EORTC study). However, we would consider the approach feasible if (1) ≥ 14 of 17 patients ($\geq 83\%$) are able to successfully undergo R0 resection within 6 weeks of last chemotherapy administration (if applicable); and (2) the rate of serious postoperative complications attributable to pembrolizumab-based treatment does not exceed 33% (6 of 17 patients).

The study will also use descriptive statistics to compare 2-year RFS rates in patients who do or do not receive adjuvant pembrolizumab-based therapy.

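### Section 8.4.1 leaves treated but unresected patients out of the R0 resection rate, and its denominator is not reconciled with the 14-of-17 feasibility rule in 8.4.3

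*Combined protocol and SAP*

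**What the plan says.** Section 8.4.1 sets the evaluable patients endpoint by endpoint. For the surgical endpoints it says: "Patients who undergo surgical resection of liver metastases will be evaluable for the secondary clinical efficacy endpoints: pathologic response rate, R0 resection rate", and it adds 2-year RFS to that list. For the remaining efficacy endpoint the set is wider: "The All Patients as Treated (APaT) population will be used for the analysis of the secondary safety/toxicity outcomes and the clinical efficacy endpoint, ORR". APaT requires at least one dose of either drug and at least one laboratory or vital-sign measurement.

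The secondary objectives in the Abstract give the purpose of the surgical endpoints as "response to pembrolizumab plus vactosertib as measured by R0 resection rate; pathologic response". Section 2.3 starts the efficacy time frame at baseline, not at surgery. Section 7.1 defines pathologic response by the residual cancer cells in the resection specimen and does not name a denominator.

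Section 8.4.3 calls the approach feasible if at least 14 of 17 patients (stated as at least 83%) "are able to successfully undergo R0 resection within 6 weeks of last chemotherapy administration (if applicable"), together with a limit on serious postoperative complications. It does not say whether the 17 are treated, TIL-evaluable or resected patients.

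On numbers, 8.2.2 says: "We plan to enroll 19 patients to achieve our goal of 17 patients evaluable for the primary study outcome". Sections 3.2, 5.1.4 and 8.3 have rules on lost or delayed surgery and surgical complications in the first six patients. Section 6.1.4 asks for a second liver biopsy when surgery is canceled. No section says that an unresected patient counts as not R0.

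**The concern.** Whether a patient reaches surgery is known only after study treatment has begun, and it may depend on that treatment through toxicity or progression. Restricting the R0 rate to resected patients conditions on that event. What remains is the proportion of operations that achieved R0. That is a useful figure, but it does not answer the Abstract's question about response to the preoperative treatment, for which the relevant group is everyone who received it.

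The effect runs one way. The resected-only rate can equal the all-treated rate but cannot fall below it, and it can read 100% however many operations are lost. The trial enrols patients treated with curative intent, so a lost operation matters to anyone reading the R0 rate. Section 3.1 also says that later cohorts may be added on the basis of this one's results.

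**Working it through.** **Inputs.** Planned enrolment is 19, with 17 evaluable for TILs (8.2.2). The R0 denominator is resected patients (8.4.1). The feasibility count is 14 of 17 (8.4.3). The numbers of unresected patients, k, are assumptions chosen to show the range.

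**The plan's own R0 figure.** 14/17 = 82.4%, so a count of 14 falls just short of the stated 83%; 15/17 = 88.2%. The point made here does not depend on this slip.

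**Denominator effect.** Let N patients be treated, k of them unresected, and x be R0.

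- Rate under 8.4.1: x/(N-k)
- Rate among all treated: x/N
- Ratio of the two: N/(N-k)

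For N = 19, with every resected patient R0 (x = 19-k):

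| k unresected | 8.4.1 rate | All-treated rate | Ratio |
|---|---|---|---|
| 0 | 19/19 = 100% | 19/19 = 100% | 1.00 |
| 1 | 18/18 = 100% | 18/19 = 94.7% | 1.06 |
| 2 | 17/17 = 100% | 17/19 = 89.5% | 1.12 |
| 3 | 16/16 = 100% | 16/19 = 84.2% | 1.19 |
| 5 | 14/14 = 100% | 14/19 = 73.7% | 1.36 |

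Exact 95% intervals at k=3 are 79-100% for 16/16 and 60-97% for 16/19.

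**8.4.1 against 8.4.3.** Take the last row. Suppose that three of the five unresected patients have an analysable second biopsy, so that 17 are TIL-evaluable, and that all 14 R0 resections fall within the 6-week limit where it applies. The same data then give:

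- 14/14 = 100% under 8.4.1;
- 14/17 = 82.4% under 8.4.3, if its 17 are the TIL-evaluable patients;
- 14/19 = 73.7% among all treated.

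If the 17 in 8.4.3 were instead resected patients, the rule would not register lost operations at all. The text does not settle which is meant.

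**Pathologic response.** Assume six responders, N=19 and k=3. The resected-only rate is 6/16 = 37.5%, and the all-treated rate is 6/19 = 31.6%.

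**How many losses to expect.** The plan gives no rate for this trial. Section 1.3.1 says that "the majority of carefully selected patients are ultimately taken to surgery following preoperative therapy" and cites 87.3% from an earlier perioperative chemotherapy trial. If that figure is carried over as an assumption, the expected loss is 19 x 0.127 = 2.4 patients, the chance of at least one loss is 1 - 0.873^19 = 92%, and the typical ratio is 1/0.873 = 1.15.

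**The case against.** The strongest reply is that the plan does not overlook loss of surgery. The feasibility rule in 8.4.3 counts patients who achieve R0 resection against a fixed 17. That is most naturally the TIL-evaluable group, which can include unresected patients through the second biopsy. Sections 3.2, 5.1.4 and 8.3 also bring lost or delayed operations among the first six patients to review. A reader might infer from 8.4.1 alone that lost operations could go unnoticed, and the documents do not support that. Two limits remain. The early rules cover six patients only, and on surgery those in 5.1.4 and 8.3 count only problems attributed to study treatment. The 17 in 8.4.3 is undefined, and if it means the TIL-evaluable patients it can leave two of 19 outside.

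A reader might also treat pathologic response as the same error. It is not. Section 7.1 ties it to the resection specimen, so in an unresected patient it is unassessed rather than negative, and surgery may be lost for scheduling or preference. A resected-only rate is a legitimate conditional description, provided it is not read as the rate for everyone treated.

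A reader might take the better PFS of resected patients in 1.1 as evidence of this effect. In the chemotherapy arm 3-year PFS rises from 35.4% to 42.4% (ratio 1.20), but with surgery alone it rises from 28.1% to 33.1% (1.18). That reflects general selection of resected patients and says nothing specific about losses after preoperative treatment.

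The 87.3% is a weak guide. It comes from a trial with six preoperative chemotherapy cycles, whereas here resectability is confirmed at screening and surgery follows about two weeks after one cycle. Finally, ORR and specimen-based endpoints may have different denominators without either being wrong.

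**Conclusion.** The point holds for the R0 resection rate. Its denominator in 8.4.1 does not match the use made of it in the Abstract, and it is not reconciled with 8.4.3. The overstatement relative to all treated patients is N/(N-k). At the planned 19 it runs from none when everyone is resected to a factor of 1.19 with three losses and 1.36 with five. These values of k are illustrations, and replacement under 8.2.2 could take N above 19.

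For pathologic response the point is narrower: the resected-only rate is acceptable as a description of resected patients but should not stand alone. The RFS population is not in question, since RFS is measured from surgery.

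The consequence is one of reporting. 8.4.3 analyses these endpoints descriptively and calls the sample too small for comparison with historical data. No test, alpha, power or sample size depends on them. The change is worth making, but it does not threaten the trial's primary result.

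**What to change.** In 8.4.1:

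- Compute the R0 resection rate in all treated patients (APaT), and count unresected patients as not R0.
- Give the resected-only R0 rate as a supportive figure, labelled as conditional on resection.
- Keep the resected-only pathologic response rate as a conditional description, and also report it with all treated patients as the denominator.
- Leave RFS from surgery in resected patients.

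In 8.4.3, name the same treated denominator for the feasibility rule. The mismatch between 14 of 17 and 83% can be corrected in the same edit.

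The cost is about a sentence in each section. No new data are needed. The R0 rate will look slightly less favourable if any operation is lost and will be unchanged if none is.

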8.4.2 Primary Analysis (or Analysis of Primary Endpoints)

TILs will be analyzed in pre- and post-pembrolizumab-based neoadjuvant treatment tumor specimens. Testing for evidence of an increase in CD3+ T-cells will be conducted using a paired t-test and the Wilcoxon signed-rank test and results compared for consistency. Testing for a difference in the central tendency of the change in CD3+ T-cells for responders vs. non-responders under either the objective radiographic or pathological response definitions of will use a two-sample t-test and a Wilcoxon rank-sum test and results compared for consistency. All tests will be conducted at a nominal significance level of 0.05 with no adjustment for multiplicity.

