8.1 Study Endpoints

Primary endpoint: the proportion of patients with a >2 fold increase in the number of tumor infiltrating TILs cells per unit area (5 high power fields) post- vs. pre-pembrolizumab-based neoadjuvant treatment tumor specimens.

Secondary endpoints:

- **Safety:** An important secondary objective of this study is to characterize the safety and tolerability of pembrolizumab-based treatment in patients with resectable liver metastases. The safety analysis will be based on patients who experience toxicities as defined by NCI CTCAE 5.0 criteria (Appendix 3). Safety will be assessed by quantifying the toxicities and grades experienced by patients who have received pembrolizumab-based treatment, including all AEs and ECIs.

The attribution to drug, time-of-onset, duration of the event, its resolution, and any concomitant medications administered will be recorded. AEs will be analyzed including but not limited to all AEs, SAEs, and fatal AEs. Furthermore, specific immune-related AEs (irAEs) will be collected and designated as immune-related ECIs as described in Section 7.3.5.

Surgical complications will be characterized using Clavien-Dindo criteria (Appendix 4). Early stopping rules have been defined to mitigate risk of perioperative complications (see section 8.3).

- **Efficacy:** Endpoints for preliminary estimation of the clinical efficacy of pembrolizumab-based treatment in the perioperative setting for patients with CRC with resectable hepatic metastases are as follows:
 - Pathologic response rate [34]
 - R0 resection rate
 - 2-year RFS with and without adjuvant pembrolizumab-based therapy
 - Objective Response Rate

Exploratory endpoints:

- Change in T-cell repertoire in pre-neoadjuvant treatment liver biopsies vs. surgical tumor specimens as well as in blood samples from the same time-points
- Change in PD-L1 expression and other molecular markers in pre-neoadjuvant treatment liver biopsies vs. surgical tumor specimens
- Correlate changes in microbiome composition and diversity (by metagenomic sequencing and untargeted metabolomics of stool collected before, during, and after immunotherapy), with diet and lifestyle factors determined by self-reported questionnaires.
- Explore the correlation between change in tumor infiltrating TILs and T-cell repertoire.

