8.2 Determination of Sample Size and Accrual Rate**8.2.1 Sample Size and Power Estimate**

For the primary objective, there will be a binary classification (28). A patient will be considered to have a “positive response” if there is a ≥ 2 -fold increase (from pre- to post-treatment) in the number of TILs, and a “negative response” if there is < 2 -fold increase. Obtaining paired specimens from 17 patients will be sufficient to determine whether 40% or more achieve a “positive response,” compared to a null hypothesis of 10% or less. This comparison has a power of 0.91 at a significance level of 0.05 for a directional binomial test.

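### The primary analysis in Section 8.4.2 tests for any change in CD3+ cells; it never estimates or tests the primary endpoint, the proportion of patients with a 2-fold TIL rise, on which the trial was sized.

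*Combined protocol and SAP*

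**What the plan says.** **Endpoint.** Section 8.1 defines it as "the proportion of patients with a >2 fold increase in the number of tumor infiltrating TILs cells per unit area". Sections 1.3.1, 1.3.5, 2.2, 3.1 and 8.2.1 describe the same proportion, but with a cut-off of 2-fold or greater (≥2) where Section 8.1 has strictly more than 2.

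**Design.** Section 8.2.1 states "For the primary objective, there will be a binary classification". With 17 pairs of specimens, the target rate is 40%, "compared to a null hypothesis of 10% or less". The section then adds: "This comparison has a power of 0.91 at a significance level of 0.05 for a directional binomial test". Section 8.2.2 says: "We plan to enroll 19 patients to achieve our goal of 17 patients evaluable for the primary study outcome".

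**Analysis.** Section 8.4.2 is the section on analysis of the primary endpoint. Its first test is: "Testing for evidence of an increase in CD3+ T-cells will be conducted using a paired t-test and the Wilcoxon signed-rank test", with the two results compared for consistency. It then compares the change in CD3+ cells between responders and non-responders, by two-sample t-test and rank-sum test. Those responders are defined by radiographic or pathological response, not by the TIL cut-off. It closes: "All tests will be conducted at a nominal significance level of 0.05 with no adjustment for multiplicity".

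Section 8.4.1 gives the primary analysis population (patients with evaluable paired specimens). Sections 8.4.3 and 8.4.4 cover secondary and exploratory analyses and do not return to the doubling proportion.

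**The concern.** The endpoint and the sample size concern one quantity, the proportion who double, with a null value of 10%. The analysis concerns another, the centre of the paired change in CD3+ cells, with a null value of zero. A statistician who followed Section 8.4.2 to the letter would never calculate the endpoint.

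Section 1.3.1 justifies the 2-fold cut-off by saying that a doubling is biologically meaningful and that smaller changes are harder to defend for publication. A test against no change rewards exactly those smaller changes.

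Four further gaps widen the choice available once data are in:

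- No test is named as decisive, and there is no rule for a disagreement between the t-test and the signed-rank test.
- Sidedness is not stated in Section 8.4.2, whereas Section 8.2.1 is directional.
- Section 8.4.2 is the only place where CD3+ cells are named as the count to be analysed. Elsewhere the term is TILs, and Section 1.3.5 leaves the staining panels to be developed.
- The cut-off differs between Section 8.1 and the other sections.

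At stake is the trial's only primary conclusion.

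**Working it through.** **1. The plan's own power figure.** Inputs from Section 8.2.1: n = 17, p0 = 0.10, p1 = 0.40, one-sided alpha 0.05. With the arcsine approximation:

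- h = 2·arcsin(√0.40) − 2·arcsin(√0.10) = 0.726
- h·√17 = 2.993
- power = Φ(2.993 − 1.645) = 0.911

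The stated 0.91 is therefore the power of a test of the proportion. It does not describe the tests in Section 8.4.2, for which the documents give neither a mean change nor an SD.

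**2. The exact version of that test.** Let X be the number of patients who double, X ~ Binomial(17, p).

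| Reject if | Alpha at 10% | Power at 40% |
|---|---|---|
| X ≥ 4 | 0.0826 | 0.954 |
| X ≥ 5 | 0.0221 | 0.874 |

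The rule that keeps alpha at or below 0.05 is X ≥ 5 (5/17 = 29.4%). At 5/17 the exact 95% interval is 10.3% to 56.0%, and the one-sided 95% lower bound is 12.4%. No ordinary exact cut-off gives 0.91; only approximations or a randomised test do.

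**3. A contradiction that needs no model.** Suppose all 17 patients rise 1.5-fold. Every paired difference is positive, so the two-sided signed-rank p-value is 2/2^17 = 0.000015. The endpoint is 0 of 17.

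**4. Rejection at the trial's own null.** Assumption, not in the documents: D = log2(post/pre) is normal with mean μ and SD σ. Fixing P(D ≥ 1) = 0.10 gives μ = 1 − 1.2816σ. The paired t-test on D has noncentrality μ√17/σ, 16 degrees of freedom and a two-sided critical value of 2.120. For σ = 0.5: μ = 1 − 0.641 = 0.359, a geometric-mean fold of 2^0.359 = 1.28; noncentrality is 0.359 × 4.123/0.5 = 2.96; rejection probability is 79%.

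The raw-count columns come from a simulation of 4,000 replicates with log-normal baseline counts (SD of the log 0.8), two-sided 0.05.

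| σ (log2) | Mean fold | t, log scale | t, raw counts | Signed-rank, raw | Binomial ≥5/17 |
|---|---|---|---|---|---|
| 0.4 | 1.40 | 99.7% | 93% | 99% | 2.2% |
| 0.5 | 1.28 | 79% | 66% | 77% | 2.2% |
| 0.6 | 1.17 | 32% | 28% | 34% | 2.2% |

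At σ = 0.8, μ = 1 − 1.025 = −0.025, and the log-scale t-test rejects about 5% of the time, counting both directions.

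**5. Power at the alternative.** With P(D ≥ 1) = 0.40, μ = 1 − 0.2533σ. Same simulation, two-sided:

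| σ (log2) | t, raw counts | Signed-rank, raw | Binomial ≥5/17 |
|---|---|---|---|
| 1.0 | 70% | 86% | 87% |
| 1.5 | 39% | 50% | 87% |

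In these two settings the t-test and the signed-rank test disagree on significance in about 21% and 24% of simulated trials. Repeat runs move the simulated figures by one or two points.

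**6. Number of tests.** Section 8.4.2 lists 2 paired tests plus 2 two-sample tests under each of 2 response definitions: 2 + 2 × 2 = 6, each at an unadjusted 0.05.

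**The case against.** The strongest reply is that Section 8 read as a whole does specify the test. Section 8.2.1 gives the cut-off, null, alternative, alpha, direction and a binomial test, Section 8.4.1 gives the population, and nothing in Section 8.4.2 says that the paired tests replace the binomial test. The primary objective in Section 2.2 is also broad, to characterize the change in TILs, and paired tests serve it. On this reading the fault is labelling and hierarchy.

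The simulation can be challenged too. The false positives need an SD of 0.4 to 0.6 and the lost power an SD of 1.0 to 1.5, so the two harms do not occur together. At an SD of 0.8 the log-scale t-test rejects about 5% at the null and has 97% power at the alternative. If the tests are one-sided, power at an SD of 1.0 is 87% (raw t), 90% (log t) and 92% (signed-rank), so nothing is lost there. Four of the six tests address a different question, so the count of six does not measure error on the endpoint.

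Much of this stands. The intended test can be inferred, and every rejection rate for the paired tests is illustrative. But one-sided testing also raises the false-positive rate (from 79% to 88% for the log-scale t-test at an SD of 0.5), and a power loss remains at an SD of 1.5 (50% to 66%). A test named only in a power statement is not an analysis plan. If the choice between Sections 8.2.1 and 8.4.2 is left to the reader, there are several candidate primary results and no rule for choosing among them. The example in step 3 needs no SD at all.

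**Conclusion.** Section 8.4.2 is wrong as written and must be fixed. The text comparison alone settles that the primary analysis omits the primary endpoint, its null value and its test. How often the two analyses would disagree depends on a between-patient SD that the documents do not give. Under normal log2 fold changes, rejection at the 10% null ranges from 99.7% (log-scale t-test, SD 0.4) to 28% (raw-count t-test, SD 0.6), against 2.2% for the exact binomial rule, and the excess is gone at 0.8. Power at 40% falls clearly below that of the binomial rule only when the SD is large: at 1.5 for all the tests, and at 1.0 for the two-sided raw-count t-test. The stated alpha and power belong to the binomial test and cannot be claimed for the paired tests.

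**What to change.** Rewrite Section 8.4.2 so that the primary analysis is:

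- the number and proportion of evaluable patients with a post/pre TIL density ratio of at least 2.0;
- an exact one-sided binomial test against 10% at 0.05, rejecting at 5 or more of 17;
- an exact confidence interval for the proportion.

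State the threshold for other evaluable numbers. It stays at 5 from 15 to 19 patients: alpha 0.0127 and power 0.783 at 15, alpha 0.0352 and power 0.930 at 19.

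Define TILs once; if CD3+ cells per 5 high-power fields are meant, say so. Use ≥2 in every section, including 8.1. Keep the paired tests, preferably on log counts and with sidedness stated, and the responder comparisons, but label them supportive or exploratory. In Section 8.2.1, replace 0.91 with the exact power of 0.874 at an exact alpha of 0.022.

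The cost is protocol and SAP wording, with no new data or patients. The sponsor accepts a stated power slightly below 0.91, and the mean-change tests lose primary status.
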